1.0 Research Design

1.1 Purpose/Specific Aims

A. Objectives

This study will examine the feasibility, acceptability, and utility of neuroimaging technique to evaluate pre-exposure prophylaxis (PrEP) promotion messages for men who have sex with men (MSM) at risk of HIV in Baltimore, MD. The **specific aim** is:

Evaluate the effectiveness of PrEP promotion messages developed via a crowdsourcing open contest¹ by assessing neural bases of persuasion.

B. Hypotheses / Research Question(s)

This is an experimental study using neuroimaging technique to assess the persuasiveness of messages developed by a crowdsourcing open contest approach the study team conducted previously.

We hypothesize that, compared with participants viewing messages developed by a social marketing approach:

- H1. Participants viewing top messages developed via open contests will show higher brain activation in the Medial Prefrontal Cortex (MPFC) regions.
- H2. A greater proportion of participants viewing top messages developed via open contests will report increased willingness and behavioral intention to take PrEP.
- H3. A greater proportion of participants viewing top messages developed via open contests will report taking PrEP action and initiation during 30-day follow up.
- H4. Brain activation in the MPFC regions is significantly more correlated with PrEP action and initiation than self-reported message effectiveness.

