1.6 Study Variables

A. Independent Variables, Interventions, or Predictor Variables

Intervention: top three messages developed by an open contest implemented in Baltimore¹.

B. Dependent Variables or Outcome Measures

Brain activity: fNIRS detects the ratio of oxygenated (O₂HB) to deoxygenated (HHB) hemoglobin based on their optical properties, with higher ratios indicating greater neural activity. Neural tissues are relatively transparent to light in the near infrared range between 700-1000 nm, and O₂HB and HHB reflect distinct wavelengths in this range. By modulating light at different wavelengths, emitting the light on the skin-exposed areas of the cranium, and detecting that light, fNIRS measures the blood oxygenation level dependent signal (BOLD) like fMRI. Because the photons reflected from neural tissue follow a reliable 'banana-shaped' path, photodetectors can be used to measure this on the scalp. By measuring the amount of absorbed light directed at the neural tissue, we can measure the amount of O₂HB and HHB present in a region of the brain at a given time and draw inferences about the level of neural activity.

PrEP-related beliefs, willingness, behavioral intention, and behavior:

All questions will be asked to participants at baseline (only to individuals aware of PrEP), at the in-person visit after reviewing all messages, and at the 30-day follow up, except questions on PrEP action and initiation, which will only be asked at the 30-day follow up.

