1.9 Data Collection

A. Primary Data Collection

▪ **Location:**

Baseline survey: in-person data collection in a private office

Neuroimaging data and post-messaging survey: in-person data collection at the private office in a community partner/community-based organization.

30-day follow up survey: online or over the phone

• **Process of Data Collection:**

Once an individual is screened eligible, he will provide an informed consent and complete a baseline survey. An in-person visit will be scheduled, roughly a week after completing the baseline survey. During the in-person visit, participants in each group will view multiple messages on a computer screen while brain activity is recorded. After completing all messages, participants will answer questions on perceived effectiveness of the messages, self-efficacy, and willingness and behavioral intention to use PrEP. Semi-structured questions on the acceptability of fNIRS will also be asked. All participants will complete a 30-day follow up by phone call or online to assess any behavioral change.

▪ **Timing and Frequency:**

Baseline survey, in-person visit/one week after completing the baseline survey, 30-day follow up

▪ **Procedures for Audio/Visual Recording:**

N/A.

▪ **Study Instruments:**

PrEP-related beliefs, willingness, behavioral intention, and behavior:

All questions will be asked to participants at baseline (only to individuals aware of PrEP), at the 2nd visit after reviewing all messages, and at the 30-day follow up, except questions on PrEP action and initiation, which will only be asked at the 30-day follow up.

Self-efficacy: Participants will be asked, on a 4-point Likert scale ranging from strongly disagree to strongly agree, to rate their agreement with the statement “I feel confident I could take PrEP as prescribed.”

Willingness: Participants will be asked, “Suppose that PrEP is at least 90% effective in preventing HIV when taken daily. How likely would you be to take PrEP if it were available for free?” with responses ranging from “I would definitely take it” to “I would definitely not take it.”⁶⁰

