Behavioral Intention: We will assess behavioral intentions to actually begin PrEP based on a real-world situation. To do this, participants will be asked, “PrEP is currently available with a prescription from your doctor and research has shown that a majority of insurance companies cover most or all of the costs of PrEP. Do you plan to begin PrEP?” Response options range from “Yes, I will definitely begin taking PrEP” to “No, I definitely will not begin taking PrEP.”

PrEP action and initiation: Items include “Have you spoken with a provider about PrEP during the past 30 days?” and “Have you started taking PrEP during the past 30 days?”

Message-related measures:

All questions will be asked after participants finish reviewing all messages during the in-person visit.

Perceived effectiveness: Participants will be asked, on a 4-point Likert scale ranging from strongly disagree to strongly agree, to rate their agreement that the message is believable, new, unconvincing, important to them, helps them feel confident about using PrEP, would help their friends use PrEP, put thoughts in their mind about using PrEP.

Baseline survey

Socioeconomic status: We will collect data on age, highest level of education attained, housing, employment history, health insurance status, access to health care, sources and amount of personal and household income,

Sexual identity: We will use a question from our previous study which asks participants to choose from heterosexual/straight, bisexual, homosexual/gay/same-gender loving, or not sure/questioning.

Sexual history: number of sex partners, sex of the partners, condom use in the past 90 days

Social media use: Types of social media sites used for socializing, seeking sex partners, and seeking health-related information.

HIV testing history

- **Ethnographic Studies, Interviews, Or Observation:**

N/A

- **Subject Identifiers:**

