4.0 Subject Considerations

4.1 Subject Selection and Enrollment Considerations

A. Method to Identify Potential Subjects

Participants will be recruited from a range of settings, including venue based outreach at community partner sites (CBOs, health clinics), street outreach, printed and online advertisements (CBO websites or Facebook pages), and word of mouth referral.

B. Recruitment Details

Recruitment staff will assess willingness of the establishment gatekeepers to permit recruitment activities. Recruitment of participants will be conducted by research staff who will receive extensive training in ethical guidelines regarding professional conduct and in how to approach and engage potential study participants. Staff will be asked to sign a pledge to protect respondent privacy and confidentiality. Recruitment staff will have a cellular phone to contact the study PI and/or security in the event that they are concerned about their safety. Each person approached will be given a project recruitment flyer that provides basic information regarding the study. Potential participants will be given information about the nature of the study, the time involved, and informed that they will be financially reimbursed for their time. In order to reduce potential embarrassment or inadvertent disclosure of HIV or sexual behaviors the script will include the comment, "If this doesn't apply to you, please give it to someone you know."

C. Subject Screening

Participants will provide verbal consent to be screened for the study. Eligible participants will be asked to provide written consent, complete a baseline survey and scheduled for the baseline visit.

- Inclusion Criteria**

Key inclusion criteria in this study are 1) 18 years and older; 2) biological male sex at birth; 3) sexually active with men in the past 6 months; 4) never taken PrEP; 5) HIV negative; 6) reside in Baltimore City or surrounding counties; and 7) meet one of the criteria for being an appropriate PrEP candidate¹: a) in a relationship with a partner not known to be HIV-negative, b) were in a nonmonogamous relationship, c) had any condomless anal sex with a casual male partner regardless of status in the prior 6 months, or d) had a positive STI diagnosis within the prior 6 months.

- Exclusion Criteria**

N/A

D. Privacy Protections

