6.0 Data Management Plan

6.1 Data Analysis

Our primary aim in this study is to assess the effectiveness of PrEP promotion messages developed via open contest by assessing brain activation in the regions associated with persuasion (i.e., Medial Prefrontal Cortex (MPFC)), and any changes in participants' PrEP willingness, behavioral intention, initiation, and action in 30-day follow up. We will first assess whether the randomization has worked by comparing baseline demographic and confounding variables of participants in each arm using Fisher's exact test for dichotomous variables, analysis of variance (ANOVA) tests for nominal variables and normally distributed continuous variables, and Wilcoxon signed-rank tests for non-normally distributed continuous variables, with statistical significance determined at alpha=0.05. Any variable for which randomization did not result in equal proportions in each arm will be incorporated into the multivariate models as a potential confounding variable.

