Next, we will conduct primary inferential analyses to compare a) the level of neural activity in MPFC, b) increase in willingness and behavioral intention to take PrEP between baseline and 30-day follow up (yes/no), and c) PrEP action and initiation at 30-day follow up (yes/no) among participants in the three conditions. fNIRS detects the ratio of oxygenated (O₂HB) to deoxygenated (HHB) hemoglobin based on their optical properties, with higher ratios indicating greater neural activity. By modulating light at different wavelengths, emitting the light on the skin-exposed areas of the cranium, and detecting that light, fNIRS measures the blood oxygenation level dependent signal (BOLD) similar to fMRI. Because the photons reflected from neural tissue follow a reliable 'banana-shaped' path, photodetectors can be used to measure this on the scalp. By measuring the amount of absorbed light directed at the neural tissue, we can measure the amount of O₂HB and HHB present in a region of the brain at a given time and draw inferences about the level of neural activity. The level of brain activation for the top message condition compared to references will be evaluated using pairwise comparison. For the binary outcome measures, increase in willingness and behavioral intention to take PrEP and PrEP action and initiation, we will first compare proportions by conditions separately for each measurement period using standard bivariate analytic techniques such as Spearman rank-order correlations, odds ratios, and Fisher's exact test. Then we will employ generalized linear mixed

models (GLMM) to evaluate the effectiveness of top messages developed via open contest. GLMM permits us to measure the fixed effect of the top messages developed via open contest on neural activity, willingness and behavioral intention to take PrEP, and PrEP action and initiation, while allowing a random effect that accounts for within-person correlation. Given the binary nature of two primary outcomes, we will specify a logit link function for our GLMM models. Comparisons of characteristics of participants who are lost to follow-up to those who are evaluated will be conducted to assess for systematic patterns that could influence results.

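### H2's yes/no increase from baseline cannot be computed for PrEP-unaware participants and discards graded answers; a day-30 score adjusted for baseline, with a not-asked indicator, uses more of the data

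*Combined protocol and SAP*

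**What the plan says.** - **Hypothesis (1.1, H2).** "A greater proportion of participants viewing top messages developed via open contests will report increased willingness and behavioral intention to take PrEP", compared with the social-marketing arm.
- **Outcome analysed (6.1 Data Analysis).** "increase in willingness and behavioral intention to take PrEP between baseline and 30-day follow up (yes/no"). It is listed among the primary inferential analyses. The same section treats it as binary, compares proportions first (Fisher's exact test is one of the methods named), and then fits a generalized linear mixed model (GLMM) with a logit link and a within-person random effect.
- **Who answers at baseline.** Section 1.6 has the items asked "at baseline (only to individuals aware of PrEP), at the in-person visit after reviewing all messages, and at the 30-day follow up". Section 1.9 repeats this: "at baseline (only to individuals aware of PrEP), at the 2nd visit after reviewing all messages, and at the 30-day follow up". After the messages and at day 30 the items carry no awareness restriction.
- **Who may enter (4.1).** The criteria include "4) never taken PrEP; 5) HIV negative; 6) reside in Baltimore City or surrounding counties". Awareness of PrEP is not among them, and there are no exclusion criteria.
- **Response format (1.9).** Both items are graded. The top options are "I would definitely take it" for willingness and "Yes, I will definitely begin taking PrEP" for intention. The number of options is not stated.
- **Baseline adjustment (6.1).** "Any variable for which randomization did not result in equal proportions in each arm will be incorporated into the multivariate models". Adjustment for the baseline score is thus conditional on an observed imbalance.
- **Timing (1.3).** The baseline survey comes about a week before the visit at which participants are randomised.

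**The concern.** A change from baseline needs a baseline. The questionnaire's own skip rule anticipates men who do not know of PrEP, and the entry criteria admit them. Section 6.1 does not say whether they are left out, counted as not increased, or imputed. If that is decided after the data are seen, the H2 result depends on the choice.

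Independently, reducing a graded answer to increased or not increased discards information that the study has already paid to collect. In a trial of 60, whose effect estimates are meant to inform a larger study (1.5), that loss is worth avoiding.

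A secondary point is that someone already at the top option at baseline cannot increase, so can only count as no in either arm.

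**Working it through.** **1. No figure to reproduce.** The documents state no power, effect size or response rate for H2. Section 1.5 rests the 60 on the range of sample sizes in earlier studies. What follows shows direction and rough size only.

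**2. Participants without a defined outcome.** Number = 60 × unaware share. The share is assumed: 60 × 0.10 = 6; 60 × 0.20 = 12; 60 × 0.40 = 24.

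**3. Simulation inputs.** From the documents: 60 participants, half per arm, so 30 each (1.3). Alpha is taken as 0.05 two-sided; section 6.1 states 0.05 only for the baseline comparisons. Assumed: latent baseline z0 ~ N(0,1); latent day-30 value z1 = 0.6·z0 + 0.8·e + 0.2 + shift × arm; four levels cut at −1.2, −0.4 and 0.524, so the baseline top share is 1 − Φ(0.524) = 0.30; unaware participants chosen at random, with the same effect. There were 4,000 runs per cell, so the Monte Carlo standard error is at most √(0.25/4000) = 0.008.

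**4. Power at shift 0.5 / 0.7 SD, 30% at the top at baseline.**

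| Analysis | 0% unaware | 20% unaware | 40% unaware |
|---|---|---|---|
| Yes/no, Fisher, aware only | 0.163 / 0.291 | 0.154 / 0.260 | 0.114 / 0.193 |
| Yes/no, chi-square, aware only | 0.234 / 0.385 | 0.200 / 0.329 | 0.162 / 0.260 |
| Yes/no, logit adjusted for baseline, aware only | 0.289 / 0.481 | 0.227 / 0.394 | 0.160 / 0.264 |
| Day-30 score adjusted for baseline, aware only | 0.494 / 0.768 | 0.416 / 0.657 | 0.318 / 0.522 |
| Same, all participants, with not-asked indicator | same | 0.462 / 0.732 | 0.442 / 0.706 |

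Type I error of the last analysis was 0.043 to 0.056, including a case where unaware participants score 0.5 SD lower.

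**5. Where the gain comes from.** With nobody unaware and 2% at the top (lower levels of equal share), power at 0.5 SD is 0.316 for chi-square, 0.348 for the adjusted yes/no logit and 0.507 for the adjusted score. Adjusting the yes/no outcome adds 0.348 − 0.316 = 0.032; keeping the grades adds 0.507 − 0.348 = 0.159. Retaining unaware participants adds 0.462 − 0.416 = 0.046 at 20% unaware and 0.442 − 0.318 = 0.124 at 40%.

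**6. Different assumptions.** With correlation 0.5, four or five levels, 20% or 40% at the top and 0% to 40% unaware, power at 0.5 SD was 0.07 to 0.20 for Fisher, 0.11 to 0.27 for a z-test without Fisher's conservatism, and 0.40 to 0.51 for the score with indicator. The unwritten rule also matters: at 40% unaware, 20% at the top and five levels, Fisher power is 0.13 with unaware participants left out and 0.08 with them counted as no.

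**7. The top option.** At 30% top and 0.5 SD, the difference between arms is 22.5 points among those below the top, and 22.5 × 0.7 = 15.7 points overall. This compares a subgroup with the whole. Changing the top share itself, with the lower cuts held at −1.2 and −0.4, gives overall differences of 15.4, 16.9 and 11.8 points at 30%, 10% and 2% top. The difference does not rise steadily as the ceiling recedes; category spacing matters too.

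**8. If unaware participants do not respond to the messages.** At 20% unaware and 0.5 SD, the score in all participants has power of about 0.31, against about 0.40 for the score in aware participants only and 0.17 for Fisher.

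**The case against.** **The planned model may be less affected.** The bivariate tests are only the first step. The GLMM sentence in 6.1 names willingness and intention, not their increase. If repeated levels are modelled, unaware participants' answers at the visit and at day 30 could enter. This stands in part. A reader might infer that H2 yields nothing for unaware participants, but the documents do not establish that. The same paragraph calls the outcomes binary and specifies a logit link, so the grades would still be lost. The GLMM was not simulated.

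**The ceiling.** A reader might infer that participants at the top option are a separate cause of low power. Step 7 does not support that. Counting them as no is also just what an increase means, not a rule the plan writes down, and a day-30 score keeps a ceiling of its own.

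**H2 is worded as a proportion and the study is preliminary.** Both are true, and no stated power is missed. Moving to a score changes the estimand and is an improvement to choose, not the correction of a miscalculation. The missing rule for unaware participants is a gap either way.

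**The score has its own gap.** A reader might infer that it uses everyone with day-30 data. For intention that is not yet so: the item asks about plans to begin PrEP, and the documents give no code for someone who has started by day 30. Starting happens after randomisation and is hypothesised to differ by arm (H3). The present yes/no outcome shares this gap, but the fix must close it.

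**Conclusion.** The point holds on two counts that follow from the text alone: an increase from baseline cannot be computed for unaware participants, whom the criteria admit, and the yes/no form discards graded answers already collected. Leaving unaware participants out would not bias the arm comparison, because awareness is recorded before randomisation, but it would shrink the sample and narrow the population without the plan saying so.

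The adjusted score had more power than the yes/no tests in every scenario with an effect that was tried, roughly double or more at 0.5 SD with 30% at the top. Most of the gain comes from keeping the grades; the gain from retaining unaware participants depends on their responding to the messages. The top-option issue is secondary.

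Every power figure is illustrative. The unaware share, top share, number of scale points, correlation and effect size are all assumed, and the comparators are Fisher, chi-square and simple logit tests, not the planned GLMM. This is a change that should be made, with medium confidence in its size.

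**What to change.** In section 6.1:

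1. Make the main H2 analysis, separately for willingness and intention, a linear regression of the day-30 score on arm, baseline score and a prespecified indicator for not asked at baseline, with the missing baseline set to a constant such as the mean of those asked. The indicator is a valid covariate because the baseline survey precedes randomisation (1.3).
2. Add a proportional-odds model and the aware-only score as sensitivity analyses.
3. Keep the proportion with an increase by arm, as H2 is worded, as a secondary result among those with a baseline value. Report by arm the numbers not asked and the numbers at the top option at baseline.
4. Before anyone sees day-30 data by arm, fix how intention is coded for a participant who has already started PrEP, and state whether the GLMM models the change or the repeated levels.
5. Align the wording of H2 in 1.1.

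The cost is text only; no new data are needed. The downsides are that the main result becomes a score difference instead of a difference in proportions, the linear model assumes equal spacing between options, the day-30 ceiling remains, and power falls relative to the aware-only score if unaware participants do not respond. Missing day-30 data are not solved by this change.

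### The logit mixed model puts a person random effect on PrEP action and PrEP initiation, each recorded once per person, so the scale of its odds ratio and a usable interval are not secured

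*Combined protocol and SAP*

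**What the plan says.** Section 6.1 (Data Analysis) first compares proportions by arm using odds ratios and Fisher's exact test. It then assigns the evaluation of effectiveness to a generalised linear mixed model covering neural activity, willingness, intention "and PrEP action and initiation, while allowing a random effect that accounts for within-person correlation". On the link it says: "Given the binary nature of two primary outcomes, we will specify a logit link function for our GLMM models".

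The same section defines the behavioural outcome as "PrEP action and initiation at 30-day follow up (yes/no"). Section 1.6 (Study Variables) says that all belief and behaviour questions are repeated, "except questions on PrEP action and initiation, which will only be asked at the 30-day follow up", and section 1.9 (Data Collection, Study Instruments) repeats this. Section 1.9 gives one item for action (having spoken with a provider) and one for initiation: "Have you started taking PrEP during the past 30 days"?

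For willingness and intention, 6.1 defines the outcome as "increase in willingness and behavioral intention to take PrEP between baseline and 30-day follow up (yes/no"). It also speaks of comparing proportions "separately for each measurement period", and its sentence on the mixed model names willingness and intention without the word increase. Any baseline variable found to be imbalanced "will be incorporated into the multivariate models as a potential confounding variable".

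**The concern.** A person random effect describes correlation among several records from one person. Action and initiation, modelled separately, have one record each. Combining them into a single yes/no, which the reference to two primary outcomes might suggest, still leaves one record. A baseline row would not help: the inclusion criteria in 4.1 require that participants have never taken PrEP, so initiation is 0 for everyone at baseline, and action is not asked then.

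H3 rests on these outcomes. Section 1.5 says that the effect sizes from this study will feed the design of a larger trial of PrEP uptake. If an imbalance is found, the adjusted estimate would come from this model. An odds ratio of arbitrary scale, or an interval too wide to use, would be a poor input to that design.

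**Working it through.** **Inputs.** From the documents: 60 participants, half per arm, so 30 and 30 (section 1.3); one yes/no record per person for each outcome (1.6, 1.9); logit link with a person random effect (6.1). The documents give no event rates, random-effect SD, software or approximation method, so the counts, SDs and routine below are assumptions. The plan states no figure for this model that could be reproduced.

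**1. Counting parameters.** The model is P(Y=1 | arm) = E[expit(b0 + b1·arm + SD·u)], with u standard normal. Two arms with one binary record per person supply 2 free probabilities. The parameters are b0, b1 and the SD, which makes 3. The Jacobian of the probabilities has rank 2 of 3.

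**2. Flat likelihood.** For each SD, b0 and b1 can be solved to reproduce the observed proportions exactly. At 6/30 vs 12/30 the maximised log-likelihood is then always 6·ln 0.2 + 24·ln 0.8 + 12·ln 0.4 + 18·ln 0.6 = -35.2024.

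| SD held at | b1 | Conditional OR = exp(b1) | Log-likelihood |
|---|---|---|---|
| 0 | 0.981 | 2.67 | -35.2024 |
| 1 | 1.160 | 3.19 | -35.2024 |
| 2 | 1.561 | 4.76 | -35.2024 |
| 3 | 2.049 | 7.76 | -35.2024 |

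At 3/30 vs 6/30 the log-likelihood is -24.7646 throughout, and the OR runs from 2.25 to 4.68 over the same SDs.

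**3. What the data still determine.** With no arm effect, the pooled proportion is 18/60 and the log-likelihood is 18·ln 0.3 + 42·ln 0.7 = -36.6519. The likelihood-ratio statistic is 2 × (36.6519 - 35.2024) = 2.90 at every SD. With the SD held fixed anywhere from 0 to 5, the Wald z moves only from 1.67 to 1.69 (6/30 vs 12/30) and from 1.07 to 1.08 (3/30 vs 6/30). The fitted proportions do not move.

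**4. What a routine returns.** Fits of y ~ arm + (1 | person) in R lme4 glmer, with Wald intervals:

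| Assumed counts | Default Laplace | 25 quadrature points | Logistic regression |
|---|---|---|---|
| 6/30 vs 12/30 | SD near 0, OR 2.67 | SD near 0, OR 2.67 | OR 2.67 |
| 3/30 vs 6/30 | SD 47.4, OR 2.37 (0.001 to 5826), p=0.83 | SD near 0, OR 2.25 (0.51 to 9.99), p=0.29 | OR 2.25 (0.51 to 9.99) |
| 2/30 vs 6/30 | SD 47.8, OR 3.76 (0.0004 to 31588) | SD near 0, OR 3.50 (0.65 to 18.98) | OR 3.50 (0.65 to 18.98) |

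At 4/30 vs 10/30 and 3/30 vs 9/30, both mixed-model fits return an SD near 0 and the crude OR. The large SD is an artefact of the approximation. At 3/30 vs 6/30 the Laplace log-likelihood rises from -24.8 at SD 0 to -13.9 at SD 47, although the true likelihood is flat. Other starting values bring the same default fit back to SD 0 and OR 2.25.

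**5. With a covariate.** The SD is then identified, but only weakly, through the assumed logit-normal shape. In simulated trials of 60 (200 per scenario, of which 200, 191 and 196 were evaluable; one standard normal covariate with log-odds 0.5), the default fit returned an SD above 1 in 2.5% of trials at 20% vs 40%, 23% at 10% vs 30% and 46% at 10% vs 20%. In those trials the standard error of the arm effect was a median 5.2, 5.1 and 5.2 times the logistic one.

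**6. Where the random effect is estimable.** With two records per person and a visit effect the rank is 4 of 4; with three records it is 5 of 5. Stacking action and initiation as two rows per person also gives full rank: 4 of 4 with a common arm effect, 5 of 5 with item-specific effects.

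**The case against.** The strongest reply is that little is lost. The test of the arm effect is identified (step 3). Three of the five count pairs tried return the crude OR. Where the default fit fails, the point estimate is only about 5% to 7% off (2.37/2.25 = 1.05; 3.76/3.50 = 1.07). The failure belongs to one assumed approximation, and an interval of 0.001 to 5826 is hard to overlook. The study is preliminary, and its proportions, crude odds ratios and Fisher's exact test can supply effect sizes for the next trial. All of this stands, and it limits the consequence.

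A reader might infer that the mixed-model result depends on the software and not on the data, or that the model's test of the arm effect is meaningless. The documents and the arithmetic do not support that: the sign, the fitted proportions and the likelihood-ratio test come from the data. Nor is the range 2.67 to 7.76 what fits would typically report; it comes from holding the SD fixed by hand.

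It can also be said that naming action and initiation together leaves room for a joint model, which would be identified. But 6.1 describes no such model. Nor does it name software or an approximation that would rule out the failing fit.

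**Conclusion.** The point holds in a limited form. Fitted separately and without covariates, the stated model for PrEP action and PrEP initiation does not separately identify the random-effect SD and the conditional odds ratio. With covariates the SD is only weakly identified. What is not secured is the scale of that odds ratio and a usable standard error and interval. With moderate counts there may be no visible harm. With sparse counts the interval can become useless, and the simulated frequency of an inflated SD runs from 2.5% to 46%, depending wholly on assumed event rates, an assumed covariate and an assumed Laplace default.

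It would go too far to read this as an error for every outcome. For willingness and intention it applies only if the increase is analysed as one baseline-to-day-30 yes/no per person, and 6.1 leaves that open. If the repeated answers are modelled, the random effect is estimable.

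**What to change.** In 6.1:

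- For PrEP action and PrEP initiation, replace the mixed model with logistic regression without a random effect (penalised if events are sparse), alongside the planned Fisher's exact test. Alternatively, write out a joint model of the two items with its arm effects and shared random effect.
- Do the same for the increase in willingness and intention if it stays as one yes/no per person.
- Keep the mixed model only for outcomes with repeated records per person, and state which time points enter.

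One line per binary outcome giving its records per person would settle the matter. The cost is a rewording of the model statement, with no new data, visits or outcomes.
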